### 5.2 Secondary Endpoints

The following secondary endpoints will be examined:

the reduction of the side effects due to HLA-B27-associated uveitis, such as IOP assessed by Goldmann applanation tonometry (APL), cystoid macular edema (central foveal thickness – central 1 mm subfield

Statistical Analysis Plan Version no. 1.0 – 20/07/2020

Protocol Code NORFLO-ORO-16 EudraCT number NA

thickness), assessed by optical coherence tomography (OCT) Spectralis® spectralis, keratopathy, evaluated by fluorescein staining of the cornea (present/absent), and synechiae, assessed by photographic slit lamp (present/absent and if present, involving one or more quadrants; photographs shall be retained to document synechia), after treatment with NORFLO® ORO, when compared to placebo;

the improvement in uveitis-related symptoms (BCVA, symptoms like ocular pain, photophobia, floaters and blurred vision, measured by VAS) after treatment with NORFLO® ORO, when compared to

placebo;

the patients' attitude towards the treatment with NORFLO® ORO, compared to placebo, was captured by means of a questionnaire (Quick Questionnaire) specifically developed for the study on the basis of previous experiences.

These data were reported at visit 1 (baseline), at visit 2 (after 6 months) and at visit 3 (after 12 months). In case of relapse near visit 3, the data collected during the visit 3 will be replaced with the data collected during the first unscheduled visit.

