6.2 Inclusion Criteria

- 1. Subjects \geq 18 years of age at baseline Visit.
- 2. HLA-B27 positive related uveitis (acute alternating non granulomatous uveitis the uveitis shall not be in acute phase at the time of enrolment and at least 8 weeks must have elapsed after the resolution of the last uveitis attack.
- 3. Subjects with at least one autoimmune uveitis relapse (UAR) in the last year.
- 4. Written informed consent obtained from subject or subject's legal representative and ability for the subject to comply with the requirements of the study.

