10.4 Additional Unscheduled Visits in Case of Relapse

Should a relapse occur, an unscheduled visit will be performed including a complete ophthalmic evaluation. The number of cells in the AC will be determined by slit lamp, too.

Topical or systemic treatment will be prescribed to the subject according to the severity of the relapse and according to the best medical judgement.

Two following visits will be scheduled 2 and 6 weeks thereafter. During these visits a complete ophthalmic evaluation will be done.

If the subject is prescribed a systemic treatment for the relapse, he/she will be withdrawn from the study, and treated according to the best medical judgement.

If only topical treatments are prescribed, the subject will be allowed to continue the study. Depending on the onset time of the relapse it could be necessary to delay Visit 2 or Visit 3 around 2 months after the topical treatment conclusion.

Should Visit 2 be delayed, the delay will be recovered by keeping the date of Visit 3 at 12 months.

Should Visit 3 be delayed, the delay will not be recovered.

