## 11.4 Efficacy Analysis

## 11.4.1 Primary Efficacy Endpoints

The number and intensity of relapses were assessed through instrumental analysis and physical examination. These endpoints will be assessed from baseline to end of treatment.

When a relapse occurs, the data reported in the first unscheduled visit concerning the intensity of the relapse and data from LFM will be used as they are taken before the administration of both systemic and topical cortisone.

Mean and standard deviation will be used to describe the number of relapses per patient. The mean number of relapses per patient will be compared between the treatment groups using Student's t-test. ANOVA will be used to include predictive/confounding variables in the model.

In addition, a generalized linear mixed model (GLMM) with Poisson statistical distribution and with the number of relapses as dependent variable will be used to assess the effects of the treatment on reducing the number of relapses, also including in the model other potentially predicting/confounding variables.

The intensity of each relapse will be scored as mild (either trace to 1+ cell OR flare  $\leq 20$ ), moderate (2+ to 3+ cell OR Flare  $\geq 20$  and  $\leq 100$ ) and severe (4+ cell OR Hypopyon OR flare  $\geq 100$ ). For each patient, the average intensity will be estimated as the mean of the intensity of relapses observed during the study. The average and the maximum intensity will be compared between treatment groups using Student's t-test. ANOVA will be used to include predictive/confounding variables in the model. As this variable could likely be not normally distributed, Wilcoxon Mann-Whitney will be also used.

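### SAP 5.2 overwrites observed Visit 3 secondary-endpoint data with relapse-visit data when a relapse falls near Visit 3, with no window in days and no basis in the protocol

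*SAP*

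**What the plan says.** SAP 5.2 lists the secondary endpoints (IOP, macular thickness on OCT, keratopathy, synechiae, BCVA, VAS symptoms, Quick Questionnaire) and says they are recorded at Visits 1, 2 and 3. It then adds a rule whose trigger is given only as "In case of relapse near visit 3". When that applies, the SAP's instruction is that "the data collected during the visit 3 will be replaced with the data collected during the first unscheduled visit". No number of days is given, nor whether the relapse must come before or after the visit. There is no matching rule for Visit 2.

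The protocol contains no replacement rule. Under Protocol 10.4, when a relapse occurs "an unscheduled visit will be performed including a complete ophthalmic evaluation", with follow-up visits 2 and 6 weeks later. Patients treated only topically stay in the study, and for them "it could be necessary to delay Visit 2 or Visit 3 around 2 months after the topical treatment conclusion". For the last visit, "Should Visit 3 be delayed, the delay will not be recovered". Patients given systemic treatment are withdrawn.

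At entry (Protocol 6.2) the uveitis must not be acute and "at least 8 weeks must have elapsed after the resolution of the last uveitis attack". SAP 11.4.2 compares changes in IOP, OCT thickness, BCVA and VAS by ANCOVA with baseline as covariate, and keratopathy, synechiae and questionnaire items by chi-square. SAP 13 names two departures from the protocol analysis: dropping the per-eye analysis and adding nonparametric tests. The replacement rule is not among them.

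**The concern.** The rule discards an observed 12-month value and substitutes one taken when the patient presents with a relapse. Four things follow.

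- **Mixed estimand.** With a non-acute baseline, a replaced patient's change is relapse minus quiet. Everyone else's is Visit 3 minus quiet. One ANCOVA pools the two.
- **Outcome-dependent trigger.** Replacement happens because of a relapse, which is the primary outcome. An arm difference in complications or symptoms may then partly restate the relapse comparison.
- **Lost data.** Synechiae or macular oedema that develop after the first relapse visit disappear if the later Visit 3 is overwritten. Protocol 10.1 lists VAS and the Quick Questionnaire separately from the ophthalmic evaluation, and Protocol 10.4 provides only the latter at the relapse visit. Replacement may therefore exchange observed VAS and questionnaire data for missing data, and SAP 9.1.4 allows no imputation.
- **Discretion.** Without a window, someone must decide patient by patient which data enter the analysis.

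**Working it through.** **The plan's own figure.** Inputs from Protocol 14.7: difference 0.6, SD 0.7, power 80%, alpha 5% (taken as two-sided). The t-test needs 22.4 per arm, so 23 per arm or 46 in all, as stated. With 20% dropout, 46/0.8 = 57.5, so 58, against 60 recruited. This calculation concerns relapse counts. The plan claims no power for any secondary endpoint.

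**Share of patients replaced.** P(at least one relapse in w days) = 1 − exp(−rate × w/365), assuming a constant relapse rate. The rates are the planning values, 2.6 (placebo) and 2.0 (active) per year. The windows are assumptions; 10 days matches the Visit 3 tolerance in Protocol 10.3.

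| Window | Placebo | Active | Expected number of 46 |
|---|---|---|---|
| 10 days | 6.9% | 5.3% | 1.6 + 1.2, about 3 |
| 30 days | 19.2% | 15.2% | 4.4 + 3.5, about 8 |
| 60 days | 34.8% | 28.0% | 8.0 + 6.4, about 14 |

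At an assumed lower rate of 1.0 against 0.77 per year, the 60-day shares are 15.2% and 11.9%.

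**Effect on a continuous endpoint.** Assume the endpoint has SD 1 and that a replaced value is shifted by D SD. With p the share replaced in an arm, that arm's variance is 1 + p(1 − p)D². With no lasting effect, the false arm difference is D × (p placebo − p active).

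For 60 days and D = 2:
- Variances are 1 + 0.348 × 0.652 × 4 = 1.91 and 1 + 0.280 × 0.720 × 4 = 1.81, giving a pooled SD of about 1.36.
- The false difference is 2 × (0.348 − 0.280) = 0.14 SD.
- With an assumed true effect of 0.85 SD, the standardised difference is (0.85 + 0.14)/1.36 = 0.73. Multiplying by √(23/2) = 3.39 gives about 2.46. Subtracting the critical value 2.015 leaves about 0.44, which is power of about 67%.

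A simulation with 23 per arm, a 60-day window and 20,000 runs agrees:

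| Shift D | False difference, no lasting effect | Rejection, no lasting effect | Power, rates 2.6 and 2.0 | Power, both rates 2.6 |
|---|---|---|---|---|
| 0 | 0.00 | 5.2% | 81% | 81% |
| 1 | 0.06 | 5.4% | 79% | 72% |
| 2 | 0.14 | 6.4% | 67% | 53% |
| 3 | 0.20 | 6.7% | 54% | 36% |

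The last column isolates the noise. In the column before it, the false difference adds to the true one and hides part of the loss.

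For 10 days and D = 2, the variances are 1.26 and 1.20, the pooled SD is 1.11 and the false difference is 0.03. The standardised difference is 0.88/1.11 = 0.79, and 0.79 × 3.39 − 2.015 = 0.66, which is power of about 75%.

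**The case against.** The strongest reply is that the two documents need not collide. Protocol 10.4 says only that delay may be needed. A Visit 3 held about two months after topical treatment ends comes more than two months after the relapse, so that relapse may no longer count as near. On this reading the SAP rule covers only a Visit 3 kept on schedule beside an attack, and the delayed visit survives. This stands: a reader might infer that the SAP always throws away a delayed, quiet Visit 3, but the text does not settle that. The protocol does not describe the delayed visit as quiet either; that is inferred from the interval.

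A reader might also infer that every replaced value comes from an untreated attack at its peak. SAP 11.4.1 says "data from LFM will be used as they are taken before the administration of both systemic and topical cortisone", but only for relapse intensity and flare in the primary analysis. Carrying this over to the secondary endpoints is an inference, though a natural one because the visit is the same.

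The size is also open to challenge. No document gives an acute shift for any endpoint. Protocol section 1.2 calls posterior-segment involvement relatively rare and says pressure is often low but may be high, so one shift cannot fit all endpoints. The 0.85 SD effect is an assumption; it resembles the plan's 0.6/0.7 = 0.86, which belongs to relapse counts. The t-test figures do not apply to keratopathy, synechiae or the questionnaire.

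Finally, analysing Visit 3 as performed does not make every value quiet. A Visit 3 that is not delayed, or an early-withdrawal visit under Protocol 10.5, may still fall in or near an attack. That is true, but it does not rescue the rule: keeping what was observed removes the outcome-triggered overwriting.

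**Conclusion.** The concern holds for the secondary endpoints. The SAP introduces an undefined, outcome-triggered replacement that the protocol does not contain and that SAP 13 does not declare. The 12-month comparisons become a mixture of relapse-visit and Visit 3 values.

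How much this matters depends on the meaning of *near* and on the acute shift, both assumed here. At planning rates about 3 of 46 patients are affected with a 10-day window and about 14 with 60 days. At those rates the main harm is noise, with modest bias.

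It would go too far to say that the 12-month outcomes simply measure relapse timing: that is true only of replaced patients. A large false-positive rate is also not what the planning rates give. With an active rate of 0.34 per year, the post-treatment figure of the earlier study in Protocol 14.7, the same 60-day, 2 SD case gives a false difference of 0.59 SD and 34% rejection. The plan does not assume that rate.

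The primary relapse-count comparison is not touched by this rule. The change should be made before unblinding, but the point does not threaten the trial's main result.

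**What to change.** Amend the SAP before database lock:

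1. Delete the replacement sentence in SAP 5.2.
2. Analyse Visit 3 as performed, including visits delayed under Protocol 10.4, and list the actual visit day and the days since the last relapse.
3. Report relapse-visit values in a separate, labelled acute-phase table.
4. Add a sensitivity analysis that excludes or flags Visit 3 values within a pre-specified number of days of a relapse.

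If any replacement is kept, define the window in days, say how delayed visits are handled and what happens for a relapse close to Visit 2, and list the rule in SAP 13.

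The cost is a few sentences and one extra table, with no new data collection. The downside is small: some Visit 3 values will still come from during or soon after a treated relapse, and follow-up length will vary for delayed visits. The listing and the sensitivity analysis make both visible.

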### 5.3 Safety Endpoints

The safety endpoints include:

- the incidence and typology of adverse events in the NORFLO® ORO treatment group compared to placebo group;
- the use of concomitant medications:
- the changes in vital signs.

### 6. PLANNED ANALYSIS

### 6.1 Interim Analysis

No interim analysis was planned.

### **6.2** Final Analysis

Final analysis will be performed according to the protocol and to this Statistical Analysis Plan, after data cleaning operations and DB Lock is performed.

# 7. SAMPLE SIZE AND STATISTICAL POWER CONSIDERATION

With a statistical power of 80% and a significance level (alpha) of 5% and a common SD of 0.7, 46 patients are needed to observe a difference of 0.6 relapses/patients between the two treatment groups (i.e., 2 relapses/patient in the NORFLO® ORO treatment group vs. 2.6 in the placebo treatment group). To take into account a potential dropout rate of 20% over 12 months, 60 patients were recruited.

A second primary endpoint, i.e. the reduction of mean number of relapses between the year before treatment and the study period, will be examined. No formal sample size estimate was feasible on this endpoint, as it was not tested previously and no reasonable scenario can be drawn.

As the two endpoints will be assessed in a hierarchical order (first, "the mean number and intensity of relapses during the study between treatment groups" and then "the reduction of mean number of relapses between the year before treatment and the study period"), according to the "Points to consider on multiplicity issues in clinical trials", issued

Statistical Analysis Plan Version no. 1.0 – 20/07/2020 Protocol Code NORFLO-ORO-16 EudraCT number NA

by the Committee for Proprietary Medicinal Products (CPMP - 2002), no sample size adjustment for multiplicity was needed.

## 8. ANALYSIS POPULATIONS

# 8.1 Intent-to-Treat Population (ITT)

All eligible patients who are randomized into the study, receive at least one dose of the study product and have at \_\_\_\_ least a post-randomization endpoint estimate will be included in the efficacy analysis. Primary endpoints will be also analyzed in a modified Intention-to-Treat Population, where the patients with the protocol violations mentioned in the session 10.2 (Protocol Deviations) will be excluded.

## 8.2 Per-Protocol (PP) Population

No per-protocol analysis was planned.

## 8.3 Safety Population

All eligible patients who are randomized into the study and receive at least one dose of the study product will be included in the safety analysis.

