14.1 Data Sets Analyzed

All eligible patients who are randomized into the study and receive at least one dose of the study product (the Safety Population) will be included in the safety analysis. All eligible patients who are randomized into the study, receive at least one dose of the study product and have at least a post-randomization endpoint estimate (the Intention-to-Treat Population) will be included in the efficacy analysis.

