### **4.2** Treatment Administration

Sixty subjects with HLA-B27-associated uveitis were enrolled and they were divided into 2 groups, 30 received the treatment and 30 the placebo, in addition to conventional therapy. In Italy 46 patients were recruited.

Each subject received a single dose of either placebo or NORFLO® ORO two times a day for 1 year. Subjects were assigned to the treatments in a random order. Evaluations were taken at baseline (t0) and during each of the following two visits within the study (t1 6 months, t2 12 months).

Data from screened patients were reviewed to determine the subject eligibility. Subjects who met all inclusion criteria and none of the exclusion criteria were enrolled in the study and randomized to treatment.

The following treatment regimens were applied:

Statistical Analysis Plan Version no. 1.0 – 20/07/2020 Protocol Code NORFLO-ORO-16 EudraCT number NA

- NORFLO® ORO 1.7450 gr
- Placebo 1.7450 gr

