### 10.2 Protocol Deviations

A protocol violation occurs when either the subject, and/or the investigator, and/or Eye Pharma fails to adhere to significant protocol requirements affecting the inclusion, exclusion, subject safety, and primary endpoint criteria. Protocol violations for this study include, but are not limited to, the following:

- Failure to meet inclusion/exclusion criteria
- Compliance with study product regimen under 90%.

Failure to comply with Good Clinical Practice (GCP) guidelines is also a protocol violation.

Protocol deviations are minor deviations from the protocol (e.g., missing a visit window because the subject is traveling). Protocol deviations and violations will be summarized, separately for each treatment group and each study phase.

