## 11.1 Analysis datasets

All eligible patients who were randomized into the study and received at least one dose of the study product (the Safety Population) will be included in the safety analysis. All eligible patients who were randomized into the study, received at least one dose of the study product and had at least a post-randomization endpoint estimate (the Intention-to-Treat Population) will be included in the efficacy analysis. Primary endpoints will be also analyzed in a modified Intention-to-Treat Population, where the patients with the protocol violations mentioned in the session 10.2 (Protocol Deviations) will be excluded.

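### Safety and ITT sets admit only eligible patients: a dosed but ineligible patient is outside the safety tables as written, and the ITT wording conflicts with the modified ITT clause

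*SAP*

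**What the plan says.** The Safety set in SAP 8.3 is "All eligible patients who are randomized into the study and receive at least one dose of the study product". Protocol 14.1 and SAP 11.1 carry the same condition. The ITT definition in SAP 8.1 opens in the same way, "All eligible patients who are randomized into the study, receive at least one dose of the study product and have at", and goes on to require some endpoint value after randomisation. Protocol 14.1 and SAP 11.1 repeat this too. Neither document defines an all-treated or all-randomised set.

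Eligibility is described in SAP 4.2: "Subjects who met all inclusion criteria and none of the exclusion criteria were enrolled in the study and randomized to treatment". SAP 10.2 and Protocol 12 nevertheless list "Failure to meet inclusion/exclusion criteria" as a protocol violation.

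For the primary endpoints, SAP 8.1 and 11.1 add a modified ITT population, "where the patients with the protocol violations mentioned in the session 10.2 (Protocol Deviations) will be excluded".

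**The concern.** The plan expects that some randomised patients may turn out not to meet the criteria, yet it makes eligibility a condition of entry to both analysis sets. Mistakes are plausible. The Protocol synopsis places screening on the day of the baseline visit, and Protocol 10.1 completes consent, rheumatologic evaluation, the eligibility check, randomisation and dispensing within Visit 1. Several criteria rest on history or judgement: recent supplement use, time since the last attack, anticipated need for systemic drugs. An error in these may surface only later.

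For safety, the first exclusion criterion in Protocol 6.3 concerns conditions that could endanger the patient. Someone dosed despite such a condition is among those whose harms the safety comparison most needs to show. For efficacy, removing randomised patients on a judgement made afterwards weakens the randomised comparison. Neither document says who would make that judgement, when, or under what blinding.

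**Working it through.** **The plan's own figures.** SAP 7 gives a difference of 0.6, SD 0.7, 80% power, 5% alpha (taken as two-sided), 46 patients evaluable and 60 recruited. The normal approximation gives n per arm = 2 × (1.96 + 0.84)² × 0.7² / 0.6² = 21.3, so 22 per arm or 44. The exact t-test needs 23 per arm, which is 46, with power 81.1% (22 per arm gives 79.3%). Allowing for 20% dropout, 46 / 0.8 = 57.5, so 58 against the 60 stated. The sample size reproduces and is not in dispute. The point concerns definitions.

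**Two readings of the word *eligible*, applied to a patient who was randomised and dosed but failed a criterion.**

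| | A: met the criteria in fact | B: judged eligible at entry |
|---|---|---|
| Safety set (SAP 8.3) | out | in |
| ITT (SAP 8.1) | out | in, if an endpoint value exists |
| Modified ITT (SAP 8.1, 10.2) | already out; the eligibility part of the exclusion is empty | removed here |
| Work done by the word | removes patients after randomisation | none; everyone randomised had been judged eligible |

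**Safety.** No clause in either document depends on the Safety set holding ineligible patients, and none restores them. Reading A is what the sentence says, and nothing offsets it. The tables affected are the between-arm adverse event tabulations and chi-square comparisons in SAP 12.2 and Protocol 14.5. Collection is not affected: Protocol 13.4.1 records every adverse event, and Protocol 13.4.2 sends every serious one to the sponsor within 24 hours.

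**ITT.** The modified ITT clause does depend on ITT holding eligibility violators. Under A, ITT versus modified ITT cannot show what eligibility violations do to the result; the contrast reflects only the other SAP 10.2 violations, such as compliance under 90% or GCP failures. Under B, the clause works as intended. The SAP does not choose between them.

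**Size.** The documents report no number of ineligible dosed patients; call it k. Under A the Safety set is 60 − k. If k = 0, nothing changes. One patient in a planned arm of 30 is 1/30 = 3.3%. If that patient has the arm's only serious event, the tabulated rate is 0/29 = 0% instead of 1/30 = 3.3%. For an event type not seen in the arm, the upper one-sided 95% limit, 1 − 0.05^(1/n), moves only from 9.5% (n = 30) to 9.8% (n = 29). The main risk is therefore an unseen event and not lost precision.

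**The case against.** The best counter-argument is that *eligible* simply means admitted to the trial. Protocol 8.1 and SAP 4.3 use the word for the patients being randomised. Protocol 10.1 puts the criteria check before randomisation. No passage sets up a later review of eligibility to remove patients from a set. The modified ITT clause fits this reading. This largely stands for ITT: a reader might infer that an ineligible patient certainly drops out of the primary analysis, but the documents do not support that. They hold two wordings that disagree. It does not settle the safety half, because no sentence adopts the entry reading and no safety clause relies on it. On that reading the word also does nothing, so deleting it loses nothing.

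A reader might also infer that the events of such patients are lost. They are not. They are collected and reported, violations are summarised by arm (SAP 10.2), and a deviation table is planned (SAP 14). What is missing is their place in the comparative tables.

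Nor is there a basis for assuming any particular share of ineligible patients; zero is possible. The effect on the primary analysis cannot be sized, because SAP 5.1 separately restricts that analysis to patients with relapses. An ineligible patient without a relapse would be outside it anyway.

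**Conclusion.** The point holds in two parts of unequal strength. For the Safety set, the literal rule leaves dosed but ineligible patients out of the between-arm tables, and nothing in the documents corrects it. For ITT, the word contradicts the modified ITT clause; the likely intent is that ITT keeps eligibility violators, but the SAP does not say so.

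The size is zero if no ineligible patient was dosed, and otherwise 3.3% of an arm per patient, assuming the planned 30 per arm. No figure in the plan is wrong. The change should be made, because the wording errs in the direction that hides harms and correcting it costs almost nothing. It is not a flaw that undermines the trial.

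**What to change.** Delete *eligible* from the set definitions in SAP 8.1, 8.3 and 11.1, and record the departure from Protocol 14.1 in SAP 13. Protocol 14 allows the SAP to modify the planned analysis, so a SAP revision is enough. Then state:

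- Safety: all patients who took at least one dose, analysed by treatment received.
- ITT: all randomised patients in their assigned arm, including those later found to have failed an entry criterion.
- Modified ITT: a sensitivity set, and the only place where eligibility violators are removed.

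Deleting the word alone would leave the dose and endpoint-value conditions in ITT. They do not follow from the eligibility question, but the all-randomised statement above replaces them and the revised text should say so.

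Make the change before database lock and unblinding. It needs no new data. The downside is that ITT may be slightly diluted by a few ineligible patients; the modified ITT shows whether that matters.
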